13.0 Withdrawal of Subjects

Participants may refuse to take part in or stop taking part in this study at any time. Should they decide to withdraw after enrollment, they will be encouraged to contact the PI, who is also a burn surgeon, to discuss their decision and continuity of care outside of the study. Their decision not to take part in the study will not affect their current or future medical care or any benefits to which they are entitled. The investigators and/or the sponsor may stop participants' involvement in this study at any time if they decide it is in their best interest. The investigator and/or sponsor may also do this if participants do not follow the investigator's instructions.

14.0 Risks to Subjects

1. The research material obtained from human participants in this protocol will include questionnaire data and case report forms clinical data. Breaches of confidentiality are a concern with web-accessible components of any study. However, we have taken many steps to protect participant information, including only using study ID numbers on all questionnaires and storing data on secure, password-protected servers. Only the study team will be able to see this information.
2. It is possible that the questionnaires may make participants feel upset. These reactions will be normalized and appropriate resources and/or referrals to a mental health provider (outside of the study) may be provided.
3. Risks associated with TOBI vs. standard FTF burn care:
 - We do not anticipate more than minimal risk to participants in this study as study procedures closely follow those used in routine clinical care. Because the intervention includes the use of a smartphone technology in addition to standard therapy FTF therapy if needed, there is minimal risk above the risk normally incurred by undergoing standard medical treatment. A potential risk is the possibility that burn care delivered through TOBI is worse than care delivered in person (FTF). Although numerous studies suggest that the burn care can be

safely delivered through telemedicine, the TOBI intervention may not accurately portray the burn injury. In practice, the TOBI arm of the RCT includes the use of a smartphone technology in addition to standard therapy. Because patients in the TOBI arm are allowed to return in person for FTF care, there is minimal risk above the risk normally incurred by undergoing standard medical treatment. For example, it is possible that a participant might experience a burn complication at home that is not properly detected through use of the TOBI intervention. Burn complications include infection, pain, and non-healing. If there is an issue with technology, or image/video transfer is inadequate, these issues will be noted and the patient will be evaluated in the standard manner, in clinic face-to-face or in the emergency department. Patients in the standard therapy arm will be evaluated in clinic or emergency room, which is the standard of care. Nevertheless, we do have a specific protocol should a participant have an adverse event as a result of participation in this study.

- Patients in both groups will receive an initial FTF visit either in the burn clinic, hospital, or emergency department. In routine outpatient burn care, the primary risks of burn treatment include burn wound infection, non-healing, and pain. Burn wound infection is the highest risk complication, but, fortunately, is very uncommon in pediatric burn wounds. In adults, burn wound infection approaches 5% in some studies. Data of the incidence of outpatient burn wound infection in children is incomplete, although anecdotal evidence from our practice suggests that outpatient burn wound infection is extremely uncommon. In our pilot series of 32 patients treated with TOBI, none had burn wound infection. Burn wound infection would be normally assessed on visual inspection of the wound and a clinical history of fever. In order to mitigate the small, potential risk of burn infection that is misdiagnosed by using TOBI communication, each daily digital interaction (e.g., video-conferencing, or image-transfer) will be prompted with a dialogue box asking the caregiver if the patient has had a fever in the last 24 hours. This will enhance detection of fever in a burn wound infection patient. In terms of other short-term complications measured, including non-healing or pain, if there is a suspicion that these two clinical outcome measures were inadequately treated by TOBI, the patient will be requested to make a FTF visit.
- [name] is a licensed surgeon in South Carolina and has over 12 years of experience assessing and treating patients with burn injury. He will closely supervise all study staff, and will hold weekly meetings with the team during the initial recruitment of patients. He and his partners will provide burn care using both modalities, as is their current clinical practice. All burn surgeons and therapists at MUSC will undergo training in the study procedures. All staff will have cell phone numbers where Drs. [name] and [name] will be available. [name] will coordinate his schedule with staff to ensure that he is available during any staff-patient interactions. In the rare instance where he cannot be reached, [name] will serve as the clinical backup and will follow these protocols and standards.

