4.0 Study Endpoints

Primary endpoints

- Feasibility outcomes:
 - Recruitment (ratio of how many recruited vs. consented; reasons why patients chose not to do the study);
 - Participation/attrition (percentage of those consented and retained over time vs. dropouts; or benchmark for attrition is consistent with similar studies and is 20%; reasons why patients dropped out and from which condition);
 - TOBI treatment fidelity (providers' adherence to the treatment protocol; will use a fidelity checklist each visit which will be self-rated by providers themselves and patients);
 - Safety (AE or SAE, UPs occurrence in both conditions),
 - Problems with technology (number of times problems happened, notes if TOBI did not function correctly [e.g., video breaks down]).

Secondary endpoints

- Clinical outcomes:
 - Time to treatment of wound complication (e.g., infection, pain, non-healing), patient's sleep, therapy adherence, and FTF clinical visits.
- Caregiver factors:
 - Attitudes toward telemedicine, perception of healthcare access, affect, distress/stress, depression, anxiety, self-efficacy, posttraumatic growth.
 - Satisfaction with care

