10.0 Study Design / Methods

The RCT will include 64 patient/caregiver dyads recruited from the MUSC outpatient burn clinic, hospital floor, or pediatric emergency room, randomized to burn care enhanced with TOBI (n=32) or FTF standard care (n=32). After obtaining informed consent, the research staff will create a new patient record in the REDCap database and assist (if needed) the caregiver in completing the initial questionnaire battery using the REDCap survey. The baseline questionnaires, completed by the caregiver, will include the demographics form, measures about attitudes toward telemedicine, perception of healthcare access, affect, depression, anxiety, self-efficacy, and peritraumatic distress (see measures attached). All PHI will be protected by a study ID to promote confidentiality. The family will receive a ClinCard at the beginning of the study which works like a bank debit card and can be used to purchase goods or services everywhere Debit MasterCard is accepted. Each time they receive payment for participation in this study, the money will be added to the card. Families will receive \$20 for completion of baseline assessment.

At the completion of questionnaires, caregivers will be randomly assigned to treatment conditions. Stratified permuted block randomization will be used to assign patients to either the burn care enhanced with TOBI or FTF care only (32 dyads per arm). Assignment will be stratified by provider to ensure balanced enrollment across the treatment arms regardless of numbers enrolled per provider. To minimize the likelihood that the blind will be broken, i.e. the next treatment assignment can be guessed, the block size will be varied.

Chart review will be conducted within approximately 72 hours of enrollment and data will be recorded in a chart review checklist and subsequently transferred into the database (e.g., burn mechanism, % TBSA, burn location, burn depth, date of burn injury, time to medical treatment, type of first clinical encounter [burn outpatient vs. emergency department vs. hospital discharge], and type of dressing).

Patients randomized to FTF will undergo standard burn care including a return follow-up in the burn clinic on a routine basis as prescribed by the clinical burn team (e.g., at least once per week) until the burn has healed. Healing is defined as greater than 95% epithelialization of the burn wound. This will be determined by a clinician.

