Patients randomized to burn care enhanced with TOBI will be given instructions and will be aided in downloading TOBI onto their smartphones. Patients with TOBI will be able to use standard FTF care as well. They will demonstrate an ability to use the various components of TOBI during initial visit and enrollment and will be explained how to contact the burn team through the hospital paging operator if TOBI is unavailable. Similar to the FTF group, they will be given oral and written instructions about standard burn care with routine clinical care delivered via TOBI, including a plan to interface with the burn clinicians (text messaging, videoconferencing, or image transfer) on a routine basis. TOBI patients will be scheduled for weekly videoconferencing encounters through the app until the burn has healed. Patients will be asked to come in-person if would complications are noted by a clinician (e.g., non-healing, infection). If technological problems with TOBI are encountered (e.g., video stops working), providers may switch to another secure telehealth platform to provide the necessary care and will document technology issues appropriately, as part of feasibility assessment.

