Clinical data will be collected on case report forms by the clinical care team (e.g., burn nurse, physician) and entered into the REDCap database in a coded manner by a research assistant (who is blind to the treatment condition to reduce bias during data entry) at clinically determined intervals per routine care based on clinical judgment with TOBI or FTF (see table below). The duration and number of clinical encounters for both conditions will be guided by best clinical practice and each patient's needs. On average, most burns that meet the study eligibility criteria require 2-5 visits and heal within 2-4 weeks. Case report forms will be generated with study ID only, with no identifiable PHI in order to protect patient's privacy. Data collected at intervals will include adherence to prescribed wound care, change in therapy, wound complications, day of healing, pain scores, sleep problems, unexpected return to clinic or emergency room (see Clinical Case Report Form attached). App metrics, such as number of videoconferences, number of text-messages, number of photos, and scripted messages by burn professional will be recorded by the app software and exported at the end of the study. Images of wounds will not be stored for the purposes of this study. They may be uploaded by clinical care team members into the patient's medical record as part of standard care procedures (outside of the study). Adherence to therapy will be defined as parent/patient performance of prescribed wound care through the end of treatment. Overall compliance with therapy is defined as documentation of healed burn through TOBI or FTF. Clinical data collection will continue until 1 month after the burn is diagnosed as healed by a burn physician in either condition (FTF or TOBI).

At 1-month, caregivers will be asked to complete the post-treatment questionnaires by phone or virtually using the REDCap survey, using a public link and study ID to identify their survey. This assessment will include measures about attitudes toward telemedicine, perception of healthcare access, affect, depression, anxiety, perceived stress, posttraumatic growth, treatment satisfaction, and app feasibility (TOBI only group) (see measures attached). Collected data will be entered into REDCap by the study staff. Overall, participation rate will be recorded. Families will receive \$30 following completion of post-treatment assessment.

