focus on variability and precision of estimates rather than magnitude of effect sizes. 95% confidence intervals (CIs) of the difference in mean days to healing (or treatment change/infection) between interventions will be obtained. In addition, survival distributions and their 95% CIs will be obtained for each intervention arm using the Kaplan-Meier product limit method. Further, 95% CIs for hazard ratios will be obtained using Cox proportional hazards regression to model time to healing (treatment change) as a function of the intervention. In the future RCT, generalized linear mixed models (GLMM) will be used to obtain estimates of the variances of the clinical outcomes and the covariance structure of longitudinal measures as critical input information for determination of sample size (and hence adequate power) [82, 83]. Frequency distributions of AEs and SAEs will be used to characterize each intervention group. Analyses of caregiver data will include pre- and post-treatment group differences (TOBI vs. FTF) to understand factors related to caregiver well-being and adjustment following mHealth burn treatment and possible predictors of outcomes. These analyses may include mixed design repeated measures analyses of variance (ANOVAs) and regressions.

When the study is concluded, after 6 years all records related to the study will be destroyed. Furthermore, all staff will sign confidentiality agreements, and training sessions will emphasize the critical importance of confidentiality. The likelihood that these methods will effectively protect the confidentiality of participants is considered to be extremely high. Based on our experience with previous research projects, it is believed that these procedures will be effective in protecting confidentiality of subjects and minimizing any potential risk from participation.

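### The safety endpoint does not measure missed or late-detected complications, and because the arms are assessed differently its counts by arm may understate harm under TOBI

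*Combined protocol and SAP*

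**What the plan says.** All places are in the combined protocol and SAP.

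- **Endpoint.** Section 4.0 lists among the primary feasibility endpoints "Safety (AE or SAE, UPs occurrence in both conditions"), with no word on how events are to be found. The planned analysis in Section 11.0 is "Frequency distributions of AEs and SAEs will be used to characterize each intervention group".
- **Named risk.** Section 14.0 gives the risk as care through TOBI being worse than care in person, because "the TOBI intervention may not accurately portray the burn injury". Its example is that "it is possible that a participant might experience a burn complication at home that is not properly detected through use of the TOBI intervention".
- **FTF assessment.** Section 10.0 plans a "return follow-up in the burn clinic on a routine basis as prescribed by the clinical burn team (e.g., at least once per week").
- **TOBI assessment.** Section 10.0 states that "TOBI patients will be scheduled for weekly videoconferencing encounters through the app until the burn has healed", and that "Patients will be asked to come in-person if would complications are noted by a clinician" (a misprint for wound complications). TOBI families may also use ordinary in-person care. Section 14.0 sends patients to the clinic or emergency department when an image or video is inadequate.
- **Healing.** Section 10.0 lets each arm's own route document it: "Overall compliance with therapy is defined as documentation of healed burn through TOBI or FTF".
- **Other sources of events.** In both arms the case report form records wound complications and unplanned returns, and clinical data run to 1 month after healing (Section 10.0). Section 11.0 adds a final assessment at that time without saying whether it is in person. Section 14.0 adds a fever prompt to TOBI interactions.

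**The concern.** The endpoint counts events that someone has found. In the FTF arm the finding is done by examination. In the TOBI arm it is done mainly through the app whose accuracy Section 14.0 questions. Other things equal, a complication that TOBI misses and that resolves unseen lowers the TOBI count. One that is found late is counted, if at all, without any sign that an earlier contact judged the wound uncomplicated.

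The healed call is a second route. Time to healing is one of the planned clinical outcomes in Section 11.0, and the healed call ends weekly video contact. A premature call would shorten recorded healing time in TOBI and stop scheduled surveillance. Nothing in the plan counts a healed call that is later reversed.

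Safety is part of Aim 1, and the trial exists to find measurement problems before a multicenter RCT. A reader of the finished table could not tell whether a low TOBI count means few complications or poor detection. Much of the information needed to help separate the two is already planned for collection, but no analysis combines it.

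**Working it through.** **No figure to reproduce.** The sample of 64 (32 + 32) was chosen pragmatically (Section 6.0). The plan states no event rate, power or detection rate for safety, so the arithmetic below only illustrates scale.

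**Inputs.** From the documents: n = 32 per arm (Section 10.0); infection approaching 5% in some adult studies, no pediatric rate, and 0 of 32 infections in the TOBI pilot (Section 14.0). Assumed: the detection probabilities, a 10% risk, and the share of missed events that surface later.

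**Formula.** Expected recorded events = n × true risk × detection. The probability of recording none is (1 − risk × detection)^32. The probability that TOBI records fewer than FTF comes from two independent binomial counts.

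**Equal true risk of 5%, FTF detection 100%.** FTF: 32 × 0.05 × 1 = 1.6 recorded.

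| TOBI detection | TOBI recorded | P(TOBI records none) | P(TOBI fewer than FTF) |
|---|---|---|---|
| 100% | 1.6 | 19% | 38% |
| 75% | 1.2 | 29% | 47% |
| 50% | 0.8 | 44% | 57% |
| 25% | 0.4 | 67% | 68% |

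**True risk doubled in TOBI, 50% detection.** TOBI: 32 × 0.10 × 0.5 = 1.6. FTF: 32 × 0.05 × 1 = 1.6. The recorded counts match and the doubling is hidden.

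**Allowing for late surfacing.** Effective detection = s + (1 − s) × r, where s is initial detection and r is the share of missed events that surface later. With s = 0.5 and r = 0, 0.5 or 1, it is 50%, 75% or 100%. The shortfall shrinks as more events surface and is gone only if all do.

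**Reverse case.** Equal 5% risk, FTF detection 75%, TOBI 100%: 1.2 in FTF against 1.6 in TOBI. Now TOBI looks worse.

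**What counts alone can show.** Even with perfect detection, power for 5% against 10% with 32 per arm is about 11% (two-sided 0.05, assumed). The pilot's 0/32 has an exact two-sided 95% upper limit of 1 − 0.025^(1/32) = 10.9%, and those patients were themselves treated with TOBI.

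**Do the existing sources close the gap?**

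- Unplanned returns are on the case report form but not in the Section 4.0 safety endpoint. No analysis links them to the preceding contact.
- Section 10.0 text carries clinical data to 1 month after healing. In the Section 10.0 schedule table, as it reads in the extracted copy, the case report form row has no mark at the 1-month column, and the post-treatment row does not list complications. The FTF half of the table is cut off in that copy, so this needs checking against the source.
- The fever prompt covers fever only. Section 14.0 attaches it to daily interactions while Section 10.0 schedules weekly video. The two sections must be reconciled.
- The board in Section 12.0 reviews cases with adverse events or unanticipated problems, that is, events already identified.
- The plan does not say whether every wound complication counts as an adverse event.

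**The case against.** The strongest reply is that the plan has several ways to catch a miss. A complication that progresses can appear as a serious event, an operation, an admission, an unplanned return, delayed healing or a finding at 1 month. Caregivers in the TOBI arm can come in on their own initiative, and inadequate images lead to an in-person evaluation. A reader might infer that missed complications cannot be seen at all, or that a TOBI wound is examined in person only after a clinician has noted a problem. The documents support neither reading.

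Direction is also open. TOBI adds text messages, image transfer and the fever prompt, so it could detect some events better than FTF. A reader might infer that poorer detection is established and must make TOBI look safer. That holds only if TOBI detection is in fact poorer and the missed events stay hidden.

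Finally, the study is descriptive, sets no safety threshold and, at about 1.6 infections per arm, could not support a comparison under any endpoint.

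All of this stands and limits the point. It does not remove it. The sources that could reveal a late detection are not part of the safety endpoint and are not tied to the earlier contact. An uncertain direction is a reason to measure detection.

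**Conclusion.** The point holds in a limited form. The safety endpoint does not measure missed or late-detected complications, although Section 14.0 names them as a possible consequence of TOBI. Because ascertainment differs by arm, event frequencies by arm may understate TOBI harm.

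The size is unknown. Under the assumed 50% detection it is 0.8 of 1.6 expected events at a 5% risk, less to the extent that misses surface later, and it reverses if FTF detection is the poorer. The 5% is an adult infection figure, and no detection rate comes from the documents.

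Calling a missed complication the main TOBI risk would go too far: Section 14.0 offers it as an example of worse care. This is a worthwhile, inexpensive improvement to a primary feasibility endpoint. It does not show that the trial is unsafe or its safety data worthless.

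**What to change.** Add to the safety endpoint in Section 4.0, with identical wording for both arms:

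- (a) infection, non-healing, conversion to a deeper burn, operation or admission first identified at an unscheduled clinic or emergency visit after a contact recorded as uncomplicated;
- (b) any of these first identified within 1 month after a healed call;
- (c) any healed call later reversed.

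Routine scheduled visits in either arm must be excluded from (a). If every in-person visit counted, an ordinary complication found promptly at a routine FTF visit would be labelled late. At an assumed 10% risk and 60% TOBI detection, that could give up to 32 × 0.10 = 3.2 FTF events against at most 3.2 × 0.4 = 1.3 in TOBI, which would favour TOBI by construction.

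Derive the three counts from dated case report forms that record contact modality, and from the medical record. The form is an attachment not available here, so a date or modality field may or may not need adding. Make the Section 10.0 schedule explicitly collect complications and unplanned returns at 1 month, in line with the text of Sections 10.0 and 11.0. Report the counts descriptively by arm and give them to the DSMB.

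State in Section 11.0 that a lower TOBI event count alone is not evidence of safety because ascertainment differs by arm, and that complications that never surface remain uncounted.

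The cost is one definition, one derived variable and possibly one form field. No treatment or visit changes. A few events will need a judgement on whether the earlier contact was truly uncomplicated. An event under (a) is not proof of a miss: a complication can begin after a sound contact, and an FTF family has no app through which to report it. Listing the route of discovery and the days since the last contact would help. With 32 per arm, the counts support description only.

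### The TOBI fever prompt looks back only 24 hours, but no procedure requires daily contact, so fever on days between contacts may go unasked

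*Combined protocol and SAP*

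**What the plan says.** Section 14.0 (Risks to Subjects) states: "Burn wound infection is the highest risk complication". It adds that infection is uncommon in children and would normally be "assessed on visual inspection of the wound and a clinical history of fever". To "mitigate the small, potential risk of burn infection that is misdiagnosed by using TOBI communication", it provides that each daily digital contact (videoconferencing and image transfer are the examples given) will be "prompted with a dialogue box asking the caregiver if the patient has had a fever in the last 24 hours". The question in that box therefore concerns the preceding 24 hours only.

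Section 10.0 (Study Design / Methods) sets the TOBI contact schedule. One frequency is numeric: "TOBI patients will be scheduled for weekly videoconferencing encounters through the app until the burn has healed". Other contact is described as "including a plan to interface with the burn clinicians (text messaging, videoconferencing, or image transfer) on a routine basis", with no number. The same section leaves the number and duration of encounters to clinical practice and patient need, and expects 2-5 visits and healing in 2-4 weeks for most burns. Its data collection table lists TOBI video visits and a 1-month follow-up, but no daily check-in.

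**The concern.** The look-back in Section 14.0 and the contact schedule in Section 10.0 do not clearly match. The prompt's wording presupposes daily contact, and the procedures do not require it. A caregiver whose child had a fever that ended two days before a contact would truthfully answer no.

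At stake is part of the one added safeguard that Section 14.0 names for infection misjudged through the app. Fever history is one of the two elements of infection assessment that the section gives, and it matters most when an image is hard to read. Section 14.0 itself accepts that a complication at home might not be detected through TOBI. No endpoint estimate, power or alpha is involved.

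**Working it through.** The plan states no coverage figure, so there is none to reproduce. The check compares the look-back with the contact interval.

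**Inputs from the documents**
- Look-back: 24 hours, i.e. 1 day (Section 14.0).
- Only numeric contact frequency: weekly video (Section 10.0).
- Time to healing: 2-4 weeks, i.e. 14-28 days (Section 10.0).
- Pilot: "In our pilot series of 32 patients treated with TOBI, none had burn wound infection" (Section 14.0).
- Adult infection rate: approaches 5% in some studies (Section 14.0).

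**Step 1. Share of days asked about.** With k prompted contact days a week, coverage = k/7.

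| k per week | Coverage |
|---|---|
| 1 (weekly video only) | 1/7 = 14% |
| 2 | 2/7 = 29% |
| 3 | 3/7 = 43% |
| 7 (daily) | 7/7 = 100% |

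The first row is a limiting case. The rows for 2 and 3 are illustrations; the documents do not say how often TOBI families will send images.

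**Step 2. Days not asked about, weekly video only.** Over 14 days: 14 - 2 = 12. Over 28 days: 28 - 4 = 24.

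**Step 3. What that means for a short fever.** Assumption, not in the documents: a fever lasts d days, stops by itself, and starts at a time spread evenly over the week. With contacts g days apart, the fever overlaps a 24-hour window with probability min(1, (d + 1)/g).
- g = 7: d = 1 gives 2/7 = 29%; d = 2 gives 3/7 = 43%; d = 3 gives 4/7 = 57%.
- g = 1: 100% for every d.

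A fever still present at the contact is recorded whichever question is asked.

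**Step 4. How many children could be concerned.** The exact two-sided 95% upper limit for 0 of 32 is 1 - 0.025^(1/32) = 10.9%. At that rate the expected number of infections among 32 TOBI children is 32 x 0.109 = 3.5; at the 5% adult figure it is 32 x 0.05 = 1.6. These are expected counts, not bounds. Infections missed because of the look-back would be a subset, and nothing in the documents allows that subset to be sized.

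**Step 5. Which replacement question is safe.** A question about fever since the last contact with the burn team can cover less than 24 hours. Section 10.0 allows contact through the paging operator and in-person care, and the documents describe no prompt there. After a morning call, an afternoon image transfer would ask about a few hours only. Anchoring on the last time the question was answered, with a 24-hour floor, gives a look-back of max(time since last answer, 24 hours). That is never shorter than the current one, and it covers all 7 days of the week at any contact interval, subject to recall.

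**The case against.** The strongest reply is that the Section 14.0 sentence is a matched design: daily interactions paired with a 24-hour question. The weekly schedule in Section 10.0 concerns video only, whereas Section 14.0 names image transfer as a trigger too. No document says that contact will be less than daily. This stands to the extent that the gap is conditional. It does not remove the point, because the daily expectation appears only as an adjective in the risk section and no procedure carries it out.

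The second reply is clinical. The box does not stop a clinician from asking about a longer period, images and video reach a burn expert, a complication noted by a clinician brings the child in, and TOBI families may use face-to-face care. All of this stands and keeps the matter minor.

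A reader might infer three stronger things that the documents do not support:
- *That the prompt will cover only 14% of days.* That figure needs weekly video and no other prompted contact. The one-to-three-times-a-week range in Section 2.0 describes face-to-face clinic visits and cannot stand in for TOBI contact frequency.
- *That about half or more of fevers, or of infections, would be missed.* The 29-57% range rests on an assumed fever that ends by itself, and nothing in the documents links such fevers to infection.
- *That TOBI is less safe than the face-to-face arm.* The documents describe no between-visit fever prompt for that arm at all.

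**Conclusion.** The point holds conditionally. If TOBI contact is less than daily, which Section 10.0 permits, the prompt as worded does not ask about fever on the days between contacts; at the extreme of weekly video only, 6 of 7 days are not asked about. If contact is daily, there is no gap.

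The coverage fractions follow from the stated 24 hours and the assumed contact frequency. The fever-recording probabilities also need an assumed fever duration. The number of infections that a better question would catch cannot be quantified and is likely very small. This is an optional, low-cost safety improvement.

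How quickly a yes is reviewed, and whether caregivers are told to report fever the same day, are separate clarifications. They depend on written instructions and forms that are not in the documents, and they form no part of this conclusion.

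**What to change.** In Section 14.0, keep the prompt at every videoconference or image transfer and change the question to: *Has the patient had a fever since you last answered this question (or since the initial visit, if this is the first time), and at least within the last 24 hours?*

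The edit works whether or not daily contact is intended.

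Cost: one change to the app prompt, some reliance on caregiver recall over a longer interval, and possibly a few extra in-person visits in the TOBI arm. Face-to-face visits are an Aim 2 outcome, so any such visits would count toward that outcome in one arm only; this should be kept in mind when the visit counts are read.
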